4.3 AD Sub-Study Inclusion Criteria

Study subjects must meet all of the following inclusion criteria:

- A diagnosis of mild-moderate AD as defined by the National Institute of Aging – Alzheimer's Disease and Related Disorders Association criteria
- Mild-moderate cognitive impairment, indicated by Mini-Mental Status Exam (MMSE) scores between 23 and 15 inclusive.
- Between the ages of 50 and 85
- Must be right handed as defined by the Edinburgh Handedness Inventory
- Must be proficient in English
- Must be able to understand the nature of the study, and give informed consent

4.4 AD Sub-Study Exclusion Criteria

Study subjects must not meet any of the following exclusion criteria:

- History of stroke
- History of seizure
- History of any other significant neurologic disease (e.g., ALS)
- Significant depression as defined by the Geriatric Depression Scale; subjects with scores suggesting significant depression will not be included and [name], Co-I and Neuropsychologist at the Penn Memory Center, will be available to address concerns regarding safety and provide a referral, if needed.
- Any significant medical disorder that, in the view of the investigators, could threaten the subject's ability to complete the study (e.g., cancer, significant cardiac disease)
- Any contraindications to TMS as specified in section 4.2 above

Additional contraindications related to MRI include the presence of any of the following devices:

1. Cardiac pacemaker
2. Other programmable implanted devices, e.g., for the carotid sinus, insulin pumps and nerve stimulators, lead wires or similar wires
3. Optic implant

4. Implanted cardiac defibrillator
5. Aneurysm clip
6. Any electronically, magnetically, and mechanically activated implant
7. Ferromagnetic implant: coils, filters, and stents; metal sutures or staples
8. Claustrophobia
9. Metal in eye or orbit
10. Tattooed eyeliner

4.5 Subject Recruitment

Subjects will be recruited from several sources. The first source is from personal contacts within the University of Pennsylvania Health system, including neurologists, psychologists, neurosurgeons, and rehabilitation therapists. The study coordinator will receive referrals from members of UPHS who have previously agreed to identify potential individuals who meet the criteria of the database. The PI or study coordinator will then reach out to the subject or family member via in-person (i.e. at bedside), telephone, email, or letter to determine whether they wish to consent into the protocol. A second source is from the Penn Institute of Rehabilitation Medicine (PIRM). The study coordinator will have access to the medical charts of inpatients at PIRM and will prospectively and retrospectively review charts to determine if patients match the inclusion criteria of the protocol. Another source will be the Penn Data Store, where the study coordinator will review patient charts using the Cohort Explorer and Pennseek tools offered by the Penn Data Analytics team. Cohort Explorer will be used to identify patients that meet our inclusion/exclusion criteria. We will also use Pennseek to search free text within their chart for clinical impairments germane to currently recruiting studies (e.g. "aphasia", "stroke"). The study coordinator will send our query to the Penn Data Store, and work with the Penn Data Analytics team to refine our request. The study coordinator will request the names, telephone numbers, and addresses of patients. This data request will be automatically generated on a monthly basis. Another source is from subjects already enrolled in the Center for Cognitive Neuroscience (CCN) Focal Lesion Database (FoLD) or already listed in the FoLD Recruiting Database (covered by Protocol #824122). Whenever a researcher requests a subject enrolled into the FoLD Database under Protocol #824122, the Patient Coordinator will invite that patient to continue their participation in the database under the current protocol.

PWA will also be recruited from the Moss Rehab Research Institute (MRRI); [name] is a co-investigator at MRRI, and along with [name] CCC-SLP will recruit approximately 8-9 subjects with chronic aphasia annually.

Finally, [name], a consultant to the project, will refer potential participants from the Saffran Aphasia Center at Temple University. These potential subjects will then be contacted by study personnel.

Flyers will be posted at the clinics and rehabilitation centers noted above. All flyers will be submitted to the IRB for approval before use. Radio advertisements will be broadcasted either over conventional radio or via podcasts. All radio/podcast copy will be submitted to the IRB for approval before use.

Flyers will also be posted on social media (Facebook, Twitter, etc.). These will be one-way ads. No communication with potential subjects will be conducted on social media. All social media postings that include information or language besides the already approved flyers will be submitted to the IRB for approval before use.

4.6 AD Sub-Study Recruitment

Subjects will be recruited from the large, well-characterized research cohort of the Penn Memory Center, the clinical arm of the NIA-supported Penn Alzheimer Disease Research Center (ADRC). Drs. [name], Director of the Clinical Core of the Penn ADRC, and [name], Director of Neuropsychology in the Penn ADRC, are Co-Is on the project.

4.7 *Duration of Study Participation*

The duration of the study as outlined above is approximately 7-8 months.

4.8 *Total Number of Subjects and Sites*

We intend to enroll up to 83 subjects to achieve an evaluable sample size of 75. This attrition estimate is based on past experience.

4.9 *AD Sub-Study Total Number of Subjects*

We intend to enroll up to 30 subjects. Given our historical attrition rate, we expect attrition of approximately 15%

4.10 *Vulnerable Populations:*

Children, fetuses, neonates, or prisoners are not included in this protocol.

Although there is no known risk of TMS to the fetus, the issue has not been fully addressed; consequently, pregnant women will be excluded. All women of childbearing age (that is, not postmenopausal) will be asked to undergo a pregnancy test at the beginning of study visits. Prisoners will not be recruited. As the technique has not been studied in children, only subjects 18 and older will be permitted to participate.

5 Study Intervention (Study drug, device, biologic, vaccine, food etc.)

5.1 *Description*

We will use a MagVenture MagPro X100 with a C-B60 Butterfly Coil or Cool-B65 A/P Butterfly Coil. A sham MagVenture TMS coil (Cool-B65 A/P Butterfly Coil) that looks and sounds like the active coil but does not generate a magnetic field will be used for the sham TMS. Current stimulation surface electrodes are placed on the skin at the site of the coil which provide a small amount of current stimulation to simulate TMS.

We will use the MagVenture MagPro X100 with subjects in the AD sub-study. We will also make use of the Magstim Standard Rapid Package with an air-cooled figure-of-eight coil.

5.2 *Intervention Regimen*

Pertinent parameters for consideration in any TMS study include the location, frequency, intensity, and duration of brain stimulation.

5.2.1 **Stimulation Location**

TMS will be delivered to the right inferior pars triangularis of the contralesional, right hemisphere (part of the inferior frontal gyrus). The stimulation site will be targeted using the Localite Frameless stereotactic system for image-guided TMS research (Localite GmbH, Bonn, Germany). This system uses infrared reflectors attached to the patient's head and brain. The stimulating coil is similarly co-registered via infrared reflectors to the patient's head and to the imaging data allowing precise control of the stimulation site.

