Secondary: To identify anatomic and behavioral predictors of response to treatment and the mechanism underlying the beneficial effect of the treatment.

Number of Subjects 30 subjects

Main Inclusion and Exclusion Criteria Proficient English speakers with mild-moderate Alzheimer Disease. Main exclusion criteria are history of stroke, seizure, or other significant neurologic disease, significant depression, and substance abuse and contraindications to TMS.

Investigational Product (drug, biologic, device, etc.) TMS will be delivered using a MagVenture MagPro X100. 30 two-second trains of 10 Hz TMS every 30 seconds at left inferior parts triangularis and at left posterior superior temporal gyrus at 100% motor threshold during 10 sessions over 2 consecutive weeks

For Device include the planned use

For Drug, food, cosmetic, etc.

include the dose,

route of

administration and

dose regimen

Duration of administration (if applicable)	10 sessions of 2 minutes overall of 10 Hz stimulation at 100% Motor Threshold
Reference therapy	There is no standard reference therapy for repetitive transcranial magnetic stimulation; this regimen has been used in many similar published studies.
Statistical Methodology	Linear Mixed Models will be used to compare the performance of subjects receiving TMS to subjects receiving sham TMS on change in WAB-AQ scores
Safety Evaluations	Subject reports of adverse events will serve as the primary measure of safety.
Data and Safety Monitoring Plan	A Data and Safety Monitoring Committee consisting of 3 individuals with experience with aphasia and/or non-invasive brain stimulation will serve as the DSMB. The BAC group, under the guidance of the faculty statisticians, will provide safety reports every six months to this monitor and the PI. These reports will be blinded as to treatment assignment, unless unblinding for individual events is requested by the DSMB. All SAEs will also be reported to the IRB.

BACKGROUND AND STUDY RATIONALE

This document is a protocol for a clinical research study. This study will be conducted in full accordance with all applicable University of Pennsylvania Research Policies and Procedures and all applicable Federal and state laws and regulations including US and international standards of Good Clinical Practice.

Introduction

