8.3.1 AD Sub-Study Sample Size and Power Determination

Given the time and budget constraints that characterize a supplement, we propose to recruit to achieve an ultimate sample size of 30; given our historical attrition rate, we expect attrition of approximately 15%. The 30 subjects will be allocated to TMS + SLT and sham TMS + SLT in a 2:1 ratio, as this will provide more information about the effects of TMS and SLT and will serve as an incentive to recruitment. As noted above, loss of efficiency associated with unequal allocation is minimal relative to a 1:1 randomization for our design.

We have no preliminary data on the basis of which to calculate power. We note, however, that the meta analysis of Chen et al. (152) found a “moderate” effect size for TMS treatment for cognitive function in subjects with AD. We also note that Lee et al. (164) found a significant group effect favoring the TMS group in a study of 27 subjects with mild-moderate AD treated for impaired cognition with TMS or sham TMS and randomized in a 2:1 ratio. This project will permit us to determine an effect size that will inform sample determination for future trials.

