8.5 Subject Population(s) for Analysis

The subject population that will be subject to analysis will be the randomized population. Subjects that are non-compliant with treatment will be encouraged to continue with follow-up and these measurements will be enter into analysis (see 8.4.1 for details on the analysis of non-compliant subjects)

9 Safety and Adverse Events

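### AD sub-study: a cap of 30 enrolled with 15% attrition does not give an ultimate 30 on the post-attrition reading, and the primary endpoint, model and scan times are not fitted to its 6- and 12-week schedule

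*Combined protocol and SAP*

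**What the plan says.** **Size.** Section 4.9: "We intend to enroll up to 30 subjects. Given our historical attrition rate, we expect attrition of approximately 15" per cent. Section 8.3.1, opening "Given the time and budget constraints that characterize a supplement", says "we propose to recruit to achieve an ultimate sample size of 30", repeats the attrition of about 15%, and continues: "The 30 subjects will be allocated to TMS + SLT and sham TMS + SLT in a 2:1 ratio". It also says: "We have no preliminary data on the basis of which to calculate power". The Sub-Study Summary prints "Number of Subjects 30 subjects" without saying whether these are enrolled or completing. For the main study, section 4.8 gives both numbers: "We intend to enroll up to 83 subjects to achieve an evaluable sample size of 75".

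**Endpoint and model time.** Sections 3.3.1 and 8.1 define the primary endpoint as WAB-AQ change from the first baseline visit to the 6-month visit. Section 8.4.1 fits a linear mixed model to the 3- and 6-month outcomes together. Neither has an AD version. The Sub-Study Summary names a mixed model for WAB-AQ change and gives no time. AD follow-up is at 6 and 12 weeks (3.2, 3.2.3, 6.4.3, 6.4.5).

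**Scan time.** Section 8.4.3, which is specific to AD, puts the post-treatment scan at 6 months. Section 6.4.5 places the repeat scan with the 12-week visits, though its sentence breaks off. Section 3.2.3 allows the scan at the 12-week visit or later. Section 3.2 gives T3 and T17.

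**The concern.** A reader cannot tell whether 30 is the number randomised or the number expected to finish. The difference is about 4 to 5 subjects at the final visit, or 6 at enrolment, in a study with only about 10 sham subjects.

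The timing gap matters more for interpretation. Section 8.3.1 says the sub-study is meant to yield an effect size for planning later trials, and an effect size needs a time point. Applied literally, the 6-month endpoint has no AD visit to supply it. Two follow-up times are left, neither ranked above the other, so the choice could be made after the results are seen. Section 1.2.2.1 argues that the benefit of TMS in aphasia grows over time. On the plan's own reasoning, 6 and 12 weeks may not be interchangeable. The imaging analysis likewise has no single post-treatment time.

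**Working it through.** **1. Size**

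Inputs: cap 30 and attrition about 15% (4.9); ultimate size 30 and the same attrition (8.3.1); 2:1 allocation (3.2.4, 8.3.1); main study 83 enrolled and 75 evaluable (4.8).

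- Main-study comparator: 1 - 75/83 = 9.6% attrition. There, the enrolled and post-attrition numbers are distinct and consistent.
- Reading A, 30 is the enrolled and randomised number: retained = 30 x (1 - 0.15) = 25.5, so 25-26. By arm, 20 x 0.85 = 17.0 TMS and 10 x 0.85 = 8.5 sham.
- Reading B, 30 is the post-attrition number: enrolled = 30/(1 - 0.15) = 35.3, so 36. Check: 35 x 0.85 = 29.75, just short; 36 x 0.85 = 30.6. By arm, 24 x 0.85 = 20.4 TMS and 12 x 0.85 = 10.2 sham. The excess over the cap is 36 - 30 = 6.
- Thirty retained from 30 enrolled needs 0% attrition.
- Reading *approximately 15%* as 12-18% (my assumption): retained 30 x 0.88 = 26.4 down to 30 x 0.82 = 24.6; enrolled for 30 retained, 30/0.88 = 34.1 (35) up to 30/0.82 = 36.6 (37).

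Effect on precision, for illustration only: take a simple two-group comparison in SD units with half-width of the 95% interval = 1.96 x sqrt(1/n1 + 1/n2). At 20:10 this is 0.76 SD. At 17:8.5 it is 0.82 SD.

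**2. Endpoint and model time**

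One month = 365.25/12/7 = 4.348 weeks.

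| Main-study time | Weeks | Distance from AD visits |
|---|---|---|
| 3 months | 13.0 | about 1 week after week 12; about 7 weeks after week 6 |
| 6 months | 26.1 | about 14 weeks after week 12 |

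Twelve weeks against 3 months is a matter of labelling. The real gaps are that no AD visit exists at 6 months and that the 6-week visits have no place in the model.

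**3. Scan time**

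| Section | Post-treatment AD scan |
|---|---|
| 8.4.3 | 6 months |
| 6.4.5 | with the 12-week visits (sentence incomplete) |
| 3.2.3 | at the 12-week visit or later |
| 3.2 | T17 |

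Section 3.2.3 fits either of the first two. In section 6, visit 17 is a 6-week visit, so T17 read that way agrees with none of the others. The T labels may follow another count: for the main study, T5 and T22 match Figure 1, whose visit numbers differ from those in section 6.

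**The case against.** The strongest reply on size is that nothing fails if 30 is the randomised number. Section 4.9 is an explicit cap, the allocation sentence in 8.3.1 speaks of the 30 subjects being allocated, and the budget remark fits a fixed enrolment. The conflict then rests on one phrase. This stands as far as it goes: the text permits that reading. But the same phrase, followed by an attrition rate, mirrors the main-study wording in which the second number is post-attrition. The summaries do not decide it, because the main-study summary prints the post-attrition 75, not 83.

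A reader might infer that the sub-study loses power, or that only 25-26 subjects would be analysed. Neither is supported. No AD power is stated. Section 8.5 says "The subject population that will be subject to analysis will be the randomized population", and a mixed model can use a subject seen only at 6 weeks.

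On timing, a reader might infer that the plan requires a 6-month endpoint for AD and so contradicts itself. It does not say so. The documents expressly carry over the intervention (AD Sub-study Introduction), the test battery (7.5.1) and the remaining imaging details (8.4.3), but nowhere the endpoint time or the outcome model. The defect is an omission. There is also a natural mapping: section 6 gives the 12-week AD visits the numbers 18-20, the same as the main study's 6-month visits. That makes 12 weeks the likely intent, but the text never states it.

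On scans, the 12-week statement in 6.4.5 is incomplete and 3.2.3 is compatible with 6 months, so that conflict is softer than the other two points.

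**Conclusion.** The point holds as a set of clarifications that should be made before analysis. On the post-attrition reading, the stated size needs 36 enrolled against a cap of 30. On the other reading, about 25-26 are expected at the final visit, about 17 TMS and 8-9 sham. The arm split assumes that all 30 enrolled are randomised and that attrition is equal by arm; the plan states neither. Under either reading 8.3.1 needs rewording or 4.9 needs changing. The effect is on precision, from about 0.76 to 0.82 SD in the illustrative half-width.

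The AD primary time is undefined: the only timed endpoint falls about 14 weeks after the last AD follow-up. The AD scan time is stated in four places that do not agree. The main trial's analysis is unaffected.

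**What to change.** 1. **Size.** Give two numbers, as section 4.8 does: up to 30 enrolled and randomised 2:1, with about 25-26 expected at the final visit (about 17 TMS and 8-9 sham under the assumptions above). Replace *ultimate* in 8.3.1 to match. This keeps the cap in 4.9 and costs only wording. If the sponsor means 30 completing, change 4.9 instead; the cap then rises by 6 (5 to 7 at the assumed 12-18% attrition).
2. **Endpoint and model.** Before unblinding, name one AD time point as primary for WAB-AQ change, and write the AD mixed model with 6 and 12 weeks as its time points. The 12-week visits are the natural counterpart of the main study's 6-month visits. This costs only wording.
3. **Scan.** Reconcile sections 3.2, 3.2.3, 6.4.5 and 8.4.3 to one AD scan time, and define the T labels. This is wording only if the scan falls at the 12-week visits; a 6-month scan could need an extra attendance.

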5.2.2 AD Sub-Study Stimulation Location

TMS will be delivered to the left inferior pars triangularis and to the left posterior superior temporal gyrus. The stimulation site will be targeted using the Brainsight frameless stereotactic system for image-guided TMS research (Rogue Research, Montreal, Canada). This system uses infrared reflectors attached to the patient's head and brain. The stimulating coil is similarly co-registered via infrared reflectors to the patient's head and to the imaging data allowing precise control of the stimulation site.

5.2.3 Stimulation Parameters

Our protocol involves repetitive TMS at a frequency of 1 Hz. According to established guidelines, the maximum safe duration of single trains of rTMS at 1 Hz using an intensity of 110% of MT is “>1800” (that is >30 minutes) (Wassermann, 1998). Working well within these guidelines, we will administer 1200 pulses in one session at 1 Hz (20 minutes) at 90% of MT. We note that recent evidence suggests that stimulation intensities as high as 120% of MT are safe in stroke patients, even when applied directly to the lesioned hemisphere (61) for a period of 10 days. Our protocol calls for stimulation at a relatively lower intensity (90% MT), applied to the undamaged hemisphere of the brain, which we feel increases the safety of the study. We also note that the stimulation parameters we propose were employed in our previous clinical trial employing rTMS (protocol #805362) in which we had no adverse events.

Prior to administering experimental TMS, we will determine the motor threshold (MT) of each patient by stimulating the motor cortex in the unaffected hemisphere. MT will be defined as the minimum percentage of machine output required to produce MEPs of at least 50 microVolts on at least 5 of 10 consecutive trials at the same location. MT will be determined by single-pulse stimulation of the motor cortex subserving the contralesional hand at a suprathreshold level and subsequently reducing the percentage of the machine output until MEPs are not identified. The coil will be placed with the handle pointing to the patient's back at about 45° from the vertical position. Following determination of MT, patients will undergo 1 Hz rTMS.

The sham TMS group will be treated in the same manner as the experimental group except that MT will not be determined for the sham group. Thus, subjects in this group will never receive TMS. Sham treatment will employ a sham coil that produces the same sound as the real coil. Additionally, surface electrodes will be placed on the scalp, which will simulate the sensation of TMS. The sham and real coils will be numbered and the coil used and the MT will be recorded for each session.

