5.3 Blinding

Participants will not be informed of their assignment to active or sham status. Sham TMS will be administered with a sham TMS coil that looks and sounds like the active coil but does not generate a magnetic field. Surface electrodes applied to the scalp during sham stimulation will simulate the sensation of TMS, therefore allowing subjects with prior experience with TMS to be blind to condition as well.

The unblinded study coordinator will keep the master file of subject assignments. This individual will administer TMS, but all other individuals in contact with the subject or their data will be unaware of group assignment. In particular, the speech-language pathologist (SLP) and the individuals administering and scoring the language measures will not be present for the administration of TMS and will be blinded with respect to subject assignment. In the case of an adverse event, the blind may be broken if the PI deems it necessary.

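### Subject blinding is not secured by the procedures described: threshold finding is confined to the active arm, and matching of coils and electrodes between arms is not specified

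*Combined protocol and SAP*

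**What the plan says.** **Motor threshold.** Section 5.2.3 first says that "we will determine the motor threshold (MT) of each patient by stimulating the motor cortex in the unaffected hemisphere". It then says that sham subjects are handled like the experimental group "except that MT will not be determined for the sham group", and that "the coil used and the MT will be recorded for each session". Section 5.2.4 has the same three statements for the Alzheimer sub-study. Section 5.4 lists the patient's MT among the entries in the TMS log.

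**Coils.** Section 5.1 states: "We will use a MagVenture MagPro X100 with a C-B60 Butterfly Coil or Cool-B65 A/P Butterfly Coil". The only sham coil it names is a Cool-B65 A/P, described as resembling the active coil in look and sound. For the Alzheimer sub-study it adds: "We will also make use of the Magstim Standard Rapid Package with an air-cooled figure-of-eight coil". No Magstim sham is described.

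**Electrodes.** Section 5.3 says: "Surface electrodes applied to the scalp during sham stimulation will simulate the sensation of TMS". Sections 5.1, 5.2.3 and 5.2.4 also mention electrodes only when describing sham. No section says whether active subjects wear them.

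**The blinding claim.** Section 5.3 presents the simulated sensation as "therefore allowing subjects with prior experience with TMS to be blind to condition as well". It also keeps the speech-language pathologist and those who give and score the language tests away from TMS delivery and unaware of assignment. No section plans a check of subject blinding.

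**The concern.** Threshold finding is a noticeable event: single pulses over the hand area of motor cortex, strong enough to evoke muscle responses. As written, every active subject has it and no sham subject does. A subject who knows that it precedes real stimulation can draw a conclusion from its presence or absence. Section 5.3 expects some TMS-experienced subjects, and section 4.2 does not exclude them. The electrodes imitate scalp sensation and do nothing about this cue.

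If subjects can guess their arm, expectation can enter the results even with blinded assessors. WAB performance depends partly on effort, the Communication Confidence Rating Scale is a self-rating, and the primary safety endpoint in section 3.3.3 is what subjects report.

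**Working it through.** **1. The texts side by side**

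| Feature | Active arm | Sham arm | Status |
|---|---|---|---|
| MT finding (5.2.3, 5.2.4) | Done | Not done | Stated difference; conflicts with the each-patient wording in the same sections |
| MT recorded (5.2.3, 5.2.4, 5.4) | Value exists | No value exists | Contradiction to reconcile; a blank entry would show the arm to anyone reading the log |
| Coil, main study (5.1) | C-B60 or Cool-B65 A/P | Cool-B65 A/P | One sham model for two possible active models |
| Coil, Alzheimer sub-study (5.1) | MagVenture; Magstim also to be used | No Magstim sham named | Purpose of the Magstim equipment not stated |
| Scalp electrodes (5.1, 5.2.3, 5.2.4, 5.3) | Not specified | Worn | Silence, not a stated difference |

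Only the first row is an explicit difference in what subjects undergo. The coil and electrode rows are gaps in the specification.

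**2. The plan's own figures**

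Section 8.3 gives α = 0.05 (sidedness not stated; two-sided assumed), 80% power for 0.7 SD, an SD of change of 5.7 points, and 75 evaluable subjects at 2:1, hence 50 and 25.

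- Power by the exact noncentral t, 50 against 25, at 0.7 SD: 80.5%. The stated 80% reproduces.
- 0.7 × 5.7 = 3.99, matching the stated 4 points.

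The sample size calculation is not affected by this point.

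**3. Illustration of what expectancy could do (main study)**

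The documents give neither the share of subjects who would infer their arm nor the effect of doing so. I assume that 10% to 30% infer it and that expectancy is worth 2 WAB-AQ points. The net between-arm bias is taken as share × effect.

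- Standard error = 5.7 × √(1/50 + 1/25) = 1.396 points.
- Bias at 10%: 0.10 × 2 = 0.2 points, or 0.2/4 = 5% of the target difference.
- Bias at 30%: 0.30 × 2 = 0.6 points, or 0.6/4 = 15% of the target difference.
- Type I error = Φ(−1.96 + b/SE) + Φ(−1.96 − b/SE).
  - b = 0.2: b/SE = 0.143, error about 5.2%.
  - b = 0.6: b/SE = 0.430, error about 7.1%.

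The result depends heavily on the assumption. If the bias were 0.1, 0.2 or 0.3 SD (0.57, 1.14 or 1.71 points), the t-test would reject a true null about 6.9%, 12.7% or 22.7% of the time. None of these biases has a source in the documents.

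**The case against.** A reader might infer that blinding fails outright. The documents do not support that. A cue unblinds only those who understand it, each subject sees one arm only, and the sham is described as matched in look, sound and sensation. The primary endpoint is a performance test given and scored by blinded staff. That mitigation stands. It protects the scoring, but it does not remove a subject's own expectation.

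A reader might also infer that electrodes are worn only in the sham arm. No section says so. Section 5.2.3 names MT as the single exception to identical handling, which, read literally, points towards electrodes in both arms. The supportable statement is that the active arm is unspecified.

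On coils, section 5.1 does not say which model is for threshold finding and which for treatment, and a subject who sees one coil cannot compare two. The point is therefore a missing specification, not a demonstrated visible difference.

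Nor do the documents say how many subjects will have had TMS before. The recruitment database in section 4.5 is a focal-lesion database and one of several sources. Differential dropout is likewise conjecture: section 8.3 reports very low attrition in earlier studies.

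What survives is the explicit omission of MT finding in sham, the unmatched coil options, the silence on electrodes in the active arm, and a section 5.3 claim that none of these procedures supports.

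**Conclusion.** The point holds in limited form: subject blinding is not secured by the procedures described, and the claim about TMS-experienced subjects is unsupported. The MT difference rests on explicit text in both studies. The coil and electrode parts rest on incomplete specification. Assessor blinding is adequately described and is not in question.

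The size is unknown. The 5.2% to 7.1% range is conditional on an assumed bias of 0.2 to 0.6 points, a two-sided test, an SD of 5.7 and 50 against 25 subjects. At the lower end the error is essentially nominal. It illustrates the stake and does not estimate the bias. The changes are worth making because they are cheap and the blinding claim is made without qualification.

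**What to change.** 1. **Section 5.1:** for treatment sessions use only an active coil that has a matching sham; the Cool-B65 A/P pair is already named. State what the C-B60 and the Magstim equipment are for.
2. **Sections 5.2.3, 5.2.4 and 5.3:** state that both arms wear the same scalp electrodes, inactive in the active arm, subject to a check of the device manual.
3. **Sections 5.2.3 and 5.2.4:** run a mock threshold routine with the sham coil in the sham arm. It delivers no TMS, so the statement that these subjects never receive TMS remains true. Reconcile the each-patient wording and the MT recording text, including section 5.4, with the sham exception.
4. **Section 5.3:** qualify the claim about TMS-experienced subjects in any case. A sham coil evokes no hand response, so such subjects may still notice; the mock routine narrows the gap without closing it.
5. **Optional:** collect each subject's guess of assignment at the end of treatment and report it by arm, which would make the blinding claim testable.

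The cost is electrodes for active subjects, one short mock routine per sham subject, and a little set-up time, with equipment already on site. The sample size does not change.
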